At the time of writing, it is unclear what volume of patients have been referred to the CO@h pathway, and what onboarding data will be available due to pressure on the system to cope with the pandemic. As a result, the study may be underpowered. This risk is further exacerbated by the fact that the primary outcomes relate to use of critical care beds and mortality. The mixed-methods study of pilots of remote home monitoring models in England

found that for the pre-hospital model of CO@h, although 10% (174/1,737) of patients that were monitored deteriorated and were escalated, 0.2% (3/1,737) of patients were admitted to ICU and 1% (20/1,737) died.¹ See the Power calculation section for further details

All decisions taken after this statistical analysis protocol (SAP) has been finalised will be documented and justified in an addendum to it. We may run interim analyses on incomplete data to provide the CO@h programme team with some preliminary indications of results. The results of the final analysis will be published in line with the Health Foundation's Improvement Analytic Unit's (IAU's) aim of openness and transparency.

Study outcomes

We will analyse outcomes in the 28-day period following a COVID-19 positive test (ie equal to or less than 28 days from a positive test, with the date of the first COVID-positive test being equal to day zero). We are limiting most of the outcomes to binary variables (ie capturing whether there was an A&E attendance rather than the number of attendances); this is because of the short follow-up period and likely sparsity in hospital event counts other than 0 and 1 (which we will confirm on receipt of the data). The following outcomes will be included:

- Type 1 A&E attendance (binary outcome yes/no)
- Emergency admission (binary outcome yes/no)
- Critical care bed use (binary outcome yes/no)
 - This will capture a stay in ICU at any point during an admission, which could be as a result of either an emergency or an elective admission.
 - This variable includes level 2 and level 3 beds, as well as beds under code 5 (flexible critical care beds where there is a mix of level 2 and level 3 beds) and code 90 (temporary use of non-critical care beds).¹²
- Total emergency hospital bed days

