- **General Practice Extraction Service (GPES) Data for Pandemic Planning and Research (GDPPR)** – this data set comprises general practice data on patients registered in 97.5% of all practices in England.¹⁵ This will be the source of data on baseline characteristics for the patients included in our analysis. The age of patients (in whole weeks relative to a reference date) will be calculated by NHS Digital using this data set. From this, we will derive the age at first COVID-19 positive test (eg 65 years and 3 weeks). We will request data for patients born between 1 October 1940 (ie turning 80 on 1 October 2020, the earliest potential study start date) and 1 May 1971 (ie turning 50 on 1 May 2021).
- **Second Generation Surveillance System (SGSS)** – this system holds data on COVID-positive tests, including the full date of first COVID-positive test. SGSS is the national laboratory reporting system used in England to capture routine laboratory data (mainly on infectious diseases and antimicrobial resistance). Only the first COVID-positive test is captured in this database. We will also be provided testing data from the COVID-19 UK Non-hospital Testing Results ('pillar 2'). These sources will be used to identify our study cohort.
- **Shielded Patient List** – this data set identifies patients regarded as clinically extremely vulnerable (CEV) and at high risk of serious illness from COVID-19.
- **CO@h onboarding data** – this data set lists the date of patient onboarding (ie enrolment onto the CO@h intervention). These data will allow us to check the assumptions of a discontinuity in onboarding at age 65 and allow us to make use of a fuzzy RDD. In addition, by triangulating with hospital data, we will be able to check other assumptions – eg that onboarding is primarily occurring pre-hospital. Onboarding data were due to be collected across all CCGs from 1 December 2020, with the option of retrospectively collected data from as early as 1 October 2020 from sites that started rolling-out CO@h earlier. However, due to COVID-19 pressures, as of mid-January 2021 these patient-level data are not currently being reliably recorded nationally. Thus, the quality of this data set is a key risk to the execution and validity of the study and its ability to identify a treatment effect.

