As of 14 February 2021, there were 4,182 patients with COVID-19 symptoms within the last 14 days enrolled in the PRINCIPLE trial. We will attempt to source aggregate numbers of trial participants by age band and enrolment period, which should enable us to gauge the extent to which the two interventions are intertwined, but we would not be able to exclude trial participants, as this would introduce bias within the RDD. Therefore, we will examine the numbers of patients on PRINCIPLE and CO@h within the window of ages used in the analysis and aim to end the study period before an estimated 5% of patients in this range are likely to have been enrolled onto PRINCIPLE. This should limit the risk that these patients have a substantive effect on the outcomes of our evaluation. We may also vary the study period end date by area, depending on the roll-out of the PRINCIPLE trial, if data are available to assess this geographically. We will confirm the area-level study start and end dates and document them in an addendum to this SAP following receipt of relevant information and data.

Each patient is assigned an index date – the date of their first COVID-19 positive test – which determines the patient’s baseline and the start of their follow-up period. We will use the date of the first COVID-19 positive test rather than the date of onboarding because this allows consistent start dates for both patients who received the intervention and those who did not. This evaluation examines the effectiveness of CO@h during a 28-day period from this date, which is likely to include a period of time before patients had access to a pulse oximeter. This will allow us to evaluate the effectiveness of CO@h as it is used in practice, which may be dependent on whether pulse oximeters are distributed in time to support patients’ needs and care. We considered using the date of first onset of symptoms as the index date, as it is used by implementation teams to determine for how long oximeters should be used (ie 14 days from start of onset, unless there are signs of deterioration). However, this information is not routinely collected.

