Patients who have a COVID-19 positive test and are subsequently enrolled without any intermediate hospital activity will be considered 'treated' for the purpose of all hospital outcome analyses which occur within 28 days of the date of their first COVID-19 positive test. If a patient attends A&E after enrolment but before they received a pulse oximeter, they will still be considered as having received the intervention. This is because the evaluation seeks to understand the usefulness of CO@h as it is used in practice.

However, A&E departments are also one of the services that can refer patients to CO@h. In this case, the A&E attendance by definition pre-dates onboarding (as the pulse oximeter was dispensed following A&E attendance). Here, it is not appropriate to count the patient as having had the intervention when analysing A&E attendances. However, it is also not appropriate to exclude these patients from the analysis for outcomes that occur before onboarding, as this would introduce bias compared with patients not enrolled in CO@h. We can identify the cases described above by triangulating the date of onboarding with any dates of A&E, thereby determining whether patients were (most likely) enrolled through A&E. Using these data, we can set the intervention receipt (which is used in the fuzzy part of the design) to 1 (enrolled) or 0 (not enrolled) depending on the outcome – ie for a patient enrolled following an A&E attendance, this attendance would still count towards the outcome in the model for A&E attendances, but treatment receipt (enrolled) would be set to 0. However, for the emergency admission outcome, the same patient's subsequent emergency admission (if one occurred) would have enrolment set to 1.

Sensitivity analyses

We will undertake a range of sensitivity analyses to identify whether the resulting treatment effect estimates are reliable. These will be carried out on each of the primary outcomes (critical care bed use, total bed days in critical care, and death) but only on the secondary outcomes if these show statistically significant treatment effects. Unless otherwise stated, the design choices used in the main analysis (eg fuzzy design, window, order of polynomial, etc) will be the same as in the main analysis. The sensitivity analyses will include:

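### The outcome window opens on the test date, so the A&E visit or admission that produced the index test counts as an outcome; this costs power on two secondary outcomes, mainly Type 1 A&E attendance

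*SAP*

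**What the plan says.** Study outcomes defines the window as "equal to or less than 28 days from a positive test, with the date of the first COVID-positive test being equal to day zero". Study period, index dates and follow-up period sets the index date as "the date of their first COVID-19 positive test – which determines the patient’s baseline and the start of their follow-up period". No rule removes events dated day 0.

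The two outcomes at issue are binary: "Type 1 A&E attendance (binary outcome yes/no") and "Emergency admission (binary outcome yes/no"). Hypothesised outcomes names critical care use, critical care bed days and death as primary, so these two are secondary.

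Under Sources of data, cases come from two feeds: "SGSS is the national laboratory reporting system used in England to capture routine laboratory data", and "We will also be provided testing data from the COVID-19 UK Non-hospital Testing Results". The second is non-hospital and the first is not restricted to the community. None of the patient-level or area-level exclusions under Study cohort removes people tested on arrival at hospital.

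The section on outcomes that happen before enrolment deals with patients referred to CO@h from A&E: "this attendance would still count towards the outcome in the model for A&E attendances, but treatment receipt (enrolled) would be set to 0".

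**The concern.** A patient whose first positive swab is taken on arrival at A&E, or on the day of an emergency admission, is in the cohort and is fixed at yes by that contact. Apart from anyone already onboarded on a clinical diagnosis, nobody could have been enrolled by then. Such events should be equally common just below and just above 65 whatever CO@h does.

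Two things are at stake:

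- **Precision.** The difference at 65 keeps its size while its standard error grows. The SAP itself warns, in Study design and in Strengths and limitations, that the study may be underpowered.
- **Lost information.** A&E is a referral route into CO@h. For a patient enrolled that way, a later attendance that reassurance or an inaccurate reading might change cannot register, because the binary outcome is already yes.

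**Working it through.** **1. The SAP's own figure.** Table 1 gives N = 8,404 for a 5% baseline risk and relative risk 75% (80% power, two-sided 5%, equal groups, full compliance). The pooled-variance two-proportion formula for 5% against 3.75% returns 8,404, and all 21 cells of the table reproduce. Table 1 makes no allowance for day-0 events. The reference rates beside it, about 8% for A&E and 5% for emergency admission, describe patients already onboarded in the pilots.

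**2. Inputs for the check.**
- a = 0.08 (A&E) or 0.05 (admission): event risk after the index contact, from Power calculation.
- h = share of the cohort with a day-0 event. Not in the SAP; assumed 2%, 5% and 10%.
- r = share of day-0 patients with a further event on days 1 to 28. Not in the SAP; assumed 0 or 20%, and taken as unaffected by CO@h.

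**3. Formulas.** All patients stay in the cohort under both definitions.
- Day 0 counted: p1 = h + (1 − h)a
- Days 1 to 28 only: p0 = (1 − h)a + hr
- Under these assumptions the absolute difference at 65 is the same either way, so the ratio of N is p1(1 − p1) / [p0(1 − p0)].
- Power with day 0 counted, where days 1 to 28 would give 80%: Φ(2.80/√ratio − 1.96)

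**4. Type 1 A&E attendance.** Example at h = 5%: p1 = 0.05 + 0.95 × 0.08 = 0.126. With r = 0, p0 = 0.076 and the ratio is 0.1101/0.0702 = 1.57. With r = 20%, p0 = 0.076 + 0.010 = 0.086 and the ratio is 0.1101/0.0786 = 1.40.

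| h | p1 | p0 (r = 0) | N ratio | Power | p0 (r = 20%) | N ratio | Power |
|---|---|---|---|---|---|---|---|
| 2% | 0.0984 | 0.0784 | 1.23 | 72% | 0.0824 | 1.17 | 73% |
| 5% | 0.126 | 0.076 | 1.57 | 61% | 0.086 | 1.40 | 66% |
| 10% | 0.172 | 0.072 | 2.13 | 48% | 0.092 | 1.70 | 57% |

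**5. Emergency admission.** With r = 0, p1 = 0.069, 0.0975 and 0.145 and p0 = 0.049, 0.0475 and 0.045 at h = 2%, 5% and 10%. The ratios are 1.38, 1.94 and 2.88. With r = 20%, p0 = 0.053, 0.0575 and 0.065, and they fall to 1.28, 1.62 and 2.04.

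**6. Cross-check with a relative risk.** Suppose CO@h multiplies later A&E risk by 0.75. A cohort with no index events (8% against 6%) needs N = 5,108. Adding a 5% index share gives 12.6% against 10.7% and N = 8,950, which is 1.75 times as many. This exceeds 1.57 mainly because its comparator is a cohort without index patients, whereas step 4 keeps them. The direction is the same.

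**7. Does resetting receipt help?** No. The fuzzy analysis uses the Anderson-Rubin statistic. Under a null of zero effect the adjusted outcome is the raw outcome, so the p-value does not depend on the receipt flag. The sharp intention-to-treat analysis does not use receipt at all.

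**The case against.** **The wording may not mean day 0.** The same section speaks of the 28-day period following a positive test, and days 0 to 28 make 29 dates. No sentence states outright that day-0 events count, and the pre-enrolment section concerns attendances before onboarding on any day, so it does not settle the matter. This stands as a point about clarity. Still, the bracketed definition has no lower limit above day 0, and follow-up is said to start on the index date, so day 0 is inside the window as written.

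**Follow-up before treatment is deliberate.** The SAP accepts time before a patient has an oximeter, so as to evaluate CO@h as it is used. That justifies keeping events between test and delivery, which the fix does. It does not cover the contact at which the test was taken, which faster delivery after the test could not prevent. The SAP's bias objection is to excluding patients enrolled through A&E; one date rule applied to everyone excludes nobody.

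**Size and reach are limited.** This largely stands. h is assumed, and the result is sensitive to later events in day-0 patients. Only secondary outcomes are affected, and Hypothesised outcomes expects no marked difference in admissions.

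**The remedy is imperfect.** This also stands. The SOP as described under National roll-out of CO@h allows onboarding on clinical diagnosis, so a day-0 contact can follow enrolment. Day 1 does not isolate the index contact exactly: an admission after midnight still counts, and a separate same-day attendance after a community test is dropped. Changing the clock for admission alone would sit awkwardly with emergency bed days.

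**Stronger readings to avoid.** A reader might infer that the effect estimate is biased, or that the primary outcomes are compromised. The documents support neither: day-0 contacts are not expected to jump at 65, and the argument was made only for these two outcomes. A reader might also quote a threefold or larger rise in N. For A&E that needs h = 20% and no re-attendance (ratio 3.2, or 2.1 if 20% re-attend), and nothing in the SAP supports so high a share.

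**Conclusion.** The point holds as a loss of precision on two secondary outcomes, chiefly Type 1 A&E attendance, together with the masking of later re-attendance. The direction is clear whenever some patients have their index test at a hospital contact; the size is not known. At an assumed h of 2% to 10%, the N needed for A&E rises about 1.2 to 2.1 times with no later events in those patients, and about 1.2 to 1.7 times if 20% re-attend. An analysis with 80% power on days 1 to 28 would have roughly 72% to 48%, or 73% to 57%, with day 0 counted. These figures use onboarded pilot patients' rates as a stand-in for the cohort. For admission the proportional rise is somewhat larger, but it matters less because little effect is expected there.

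**What to change.** - **Type 1 A&E attendance:** count events on days 1 to 28 in the main analysis. Keep every patient, and keep the existing receipt rule for attendances from day 1 up to onboarding. Repeat with day 0 included as a sensitivity analysis.
- **Emergency admission:** report both the day 0 to 28 and the day 1 to 28 versions, and state that total emergency bed days still include stays that begin on day 0.
- **Day-0 contacts:** report their rate each side of 65 as an approximate pre-intervention placebo outcome, with the number of patients onboarded on or before the test date. It is only approximate because onboarding on clinical diagnosis can precede the test.

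**Cost:** two outcome definitions and a few table rows, using test, attendance, admission and onboarding dates from sources the SAP already lists. The day-0 contact of a patient already onboarded on clinical diagnosis leaves the main A&E count; the sensitivity analysis covers this. The onboarding count depends on onboarding data of adequate quality, which the SAP already flags as a risk.

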It is hypothesised that A&E attendances may go down if patients who do not need urgent care are reassured by their pulse oximetry readings and the remote support received from CO@h clinical teams. They may also go down if CO@h clinical teams are admitting patients straight to wards, bypassing A&E (although this is not expected to be a common occurrence). A&E attendances may also increase if pulse oximeters are giving inaccurate readings,^{13,14} leading to unnecessary attendances. We do not anticipate a marked difference in emergency admissions – patients on CO@h may be admitted earlier, but we would expect all patients requiring emergency admission to be admitted within the 28-day follow-up period from first positive test. If this is not the case, we may find that treated patients are more likely to experience an emergency admission. If some patients are admitted directly as a result of an inaccurate reading, this could also lead to an increase in emergency admissions. Total hospital bed days may decrease thanks to earlier escalation but could also increase if more patients survive but remain critically ill. CVWs, which is being rolled out nationally in January 2021, could also affect hospital bed days.

Sources of data

NHS Digital will provide pseudonymised, patient-level linked data from several sources. Pseudonymisation is where data sets are stripped of the personal information used for identification, such as name, full date of birth and address. A unique person identifier (such as an NHS number) is used but replaced with a consistent, randomised identifier. This identifier is used to link data sources and hospital records for the same person over time.

To further limit the patient information sourced for this study, our data set will be restricted to patients between 50–79 years of age (up to the day before their 80th birthday) at the time of their first COVID-positive test.*

The data sources used will include:

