In the current study, the running variable is age, which we will be able to determine to a weekly accuracy. Therefore, our age variable is discrete and will contain relatively few 'mass points' (ie discrete values of the running variable, shared by many subjects/patients: up to 52 mass points per year of age). In the continuity-based approach, discrete mass points represent the sampling units available for estimation (rather than the number of individual data points). Therefore, the presence of mass points greatly reduces the number of unique values available for estimation of the polynomial function. Due to the paucity of unique values of weekly age, the local randomisation approach is the logical choice in the current study. Further, there will be a week of age across which it will not be possible to determine whether the patient was (a) aged 65, or (b) just under 65 at the date of the first COVID-19 positive test; these patients will be excluded. We would expect these patients to be just as likely eligible as ineligible for CO@h, and so would not expect their exclusion to affect one group more than the other.

The local randomisation approach rests on the assumption that there is a window around the threshold where treated and control patients have the same expected outcomes and can be considered as-if randomised to treatment. Within this window, the age of the patient is assumed to be unrelated to the outcomes of interest. Although the conceptualisation of RDDs as local randomised experiments dates back many years,^{8,18} the framework for the local randomisation approach used in the current study is a relatively recent development. Our approach is based primarily on the work of Cattaneo et al.^{16,17,19,20}

Sharp and fuzzy designs

There are two RDD approaches for dealing with treatment assignment: the 'sharp' and the 'fuzzy' design. The sharp RDD assumes that the probability of treatment allocation goes from 0 to 1 at the threshold (ie that everyone below the threshold is untreated and everyone above is treated) and estimates the effect of treatment eligibility on the outcomes. This means that a sharp design can be viewed as similar to an intention-to-treat analysis in a randomised trial. In contrast, the fuzzy RDD allows for treatment compliance to be imperfect (ie for treatment receipt to differ from treatment eligibility) as long as the probability of receiving treatment still jumps abruptly at the threshold.

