4. **Check that CEV and care home patients should be excluded.** We will also check for an age-related discontinuity in onboarding of CEV and care home residents and exclude these patients from the analysis if there is no discontinuity to exploit at age 65:
 - CEV (yes/no)
 - Care home residents (yes/no)

Window selection

Although we expect there to be a trend in the proportion of patients with certain characteristics by age (eg multimorbidity, diabetes), the local randomisation approach assumes there is a window around the threshold where there are no statistically significant differences between treated and control patients. The symmetric window around the threshold that we will use in our analysis will be identified through a data-driven approach formulated by Cattaneo et al.¹⁷ The baseline variables will be exploited to identify the largest window around the age 65 threshold within which there is no evidence that the patients vary significantly between groups in terms of those baseline variables. By identifying this window, an age range is identified across which the groups of patients can be said to be comparable at baseline. These patients are then used in the main analysis to estimate treatment effects. This method assumes that the baseline variables adequately account for differences in pre-intervention characteristics within this window that might affect outcomes and vary by age. This assumption implies that the outcomes are conditionally independent of the baseline variables.

The window will be identified by first conducting tests of mean differences in the baseline variables at the narrowest window – ie 1 week either side of the age 65 threshold, and with a minimum of 10 observations (patients) per group. Each baseline variable will be tested and the smallest resulting p-value reported. The window will then be increased by 1 week either side of the threshold and the process repeated. The maximum window used in the main analysis will be the smaller of (a) the one immediately prior to the window where a statistically significant

difference between groups is first identified, or (b) the one where the sample size achieved should comfortably identify a statistically significant difference in the outcome based on power calculations*.

Although we believe that the window will be determined by (a), the criterion in (b) will ensure that any potential for unobserved confounding caused by the use of a very wide window is limited.

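### Age requested in whole weeks at a reference date makes about six days' worth of patients around 65 unclassifiable; weeks counted from the 65th birthday to the test would be equally coarse and lose none

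*SAP*

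**What the plan says.** Under Sources of data, the entry for the general practice data set states: "The age of patients (in whole weeks relative to a reference date) will be calculated by NHS Digital using this data set". The team then derives age at first positive test from that value. The testing data are more precise: "this system holds data on COVID-positive tests, including the full date of first COVID-positive test". The same section says that NHS Digital links the sources and that full date of birth is removed in pseudonymisation. It also limits the extract to people who had not reached their 80th birthday at the first positive test.

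Under Local randomisation approach, the SAP accepts the consequence: "there will be a week of age across which it will not be possible to determine whether the patient was (a) aged 65" or just below it. Those patients are excluded, on the argument that they are equally likely to fall on either side.

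Under Window selection, the search starts at "1 week either side of the age 65 threshold, and with a minimum of 10 observations (patients) per group". It widens by a week at a time and stops before the first window in which any baseline variable differs at the 0.10 level. Sensitivity analysis 4 re-estimates the effect in windows smaller than the main one. Under Study period, index dates and follow-up period, the SAP anticipates that 5 years either side will be enough.

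**The concern.** In a local-randomisation design, as-if random assignment is most credible for the patients closest to the cut-off. Most of the patients within a few days of 65 are dropped here because of the form in which age is requested. The underlying records do not force it. A variable of the same seven-day resolution, with its boundary placed at the 65th birthday, would classify every patient.

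Two steps depend on these patients. Window selection is meant to begin one week either side of 65, and the planned variable cannot deliver that window. Sensitivity analysis 4 looks at patients ever nearer the threshold, but most of the nearest have already gone. The SAP's justification deals with balance between the groups. It does not deal with the loss of patients at the cut-off or the wider age gap.

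**Working it through.** **Inputs.** From the SAP: age in whole weeks at a reference date, exact test date, first window of 1 week either side, stopping level 0.10, nine listed baseline variables, anticipated window of 5 years. Assumed: one common reference date (the SAP says a reference date, not a fixed one) and an even spread of patients over days of age near 65.

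**1. The SAP's own figure, a week of age.** With age known in whole weeks, seven birth dates are possible. A patient is unassignable if those seven put the 65th birthday on both sides of the test date. Let x be true days from the 65th birthday at test. Over the seven equally likely alignments, the number in which the patient is unassignable is:

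| x (days) | -7 | -6 | -5 | -4 | -3 | -2 | -1 | 0 | 1 | 2 | 3 | 4 | 5 | 6 |
|---|---|---|---|---|---|---|---|---|---|---|---|---|---|---|
| of 7 | 0 | 1 | 2 | 3 | 4 | 5 | 6 | 6 | 5 | 4 | 3 | 2 | 1 | 0 |

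The sum is 42, and 42/7 = 6 days' worth of patients, which agrees with the SAP's approximate week. On the birthday or the day before, 6/7 = 86% are lost. A simulation of 300,000 birth-date and test-date pairs for each of three assumed reference dates gave 5.8 to 6.0 days' worth. The loss was close to balanced (for example 1,524 above and 1,574 below).

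**2. Share of a true window of k weeks either side.** The window holds 14k days, so the share lost is 6/(14k):

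| k (weeks) | 1 | 2 | 4 | 8 | 13 | 52 | 260 |
|---|---|---|---|---|---|---|---|
| lost | 43% | 21% | 11% | 5% | 3% | 0.8% | 0.2% |

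**3. Age gap in the first window.** If only unassignable patients are dropped, the nearest retained weeks cover -13 to -1 days (mean -7) and 0 to 12 days (mean +6), a gap of 6 - (-7) = 13 days. With weeks counted from the 65th birthday they cover -7 to -1 (mean -4) and 0 to 6 (mean +3), a gap of 7 days.

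**4. Can the stopping rule select narrow windows?** With nine independent tests at 0.10 and no true imbalance, the chance that at least one is significant in a given window is 1 - 0.9^9 = 0.61. I simulated nested windows widening by equal weekly increments (nine independent normal test statistics, 40,000 runs). The rule ended at 8 weeks or fewer in 97% of runs. That figure includes the 62% of runs that already failed at the first window. Among runs that gave any window, (0.974 - 0.616)/(1 - 0.616) = 93% ended at 8 weeks or fewer. Correlated covariates would soften this. Real age trends, or several categories tested per variable, would sharpen it.

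**5. The alternative.** Completed weeks from the 65th birthday to the test, with negative values below 65, left 0 unassignable and 0 misclassified in the 300,000 pairs for each reference date. With the test date known, each value still leaves seven possible birth dates, the same as the planned variable.

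**The case against.** The SAP discloses the exclusion and gives a reason. A reader might infer that dropping these patients biases the comparison. The documents do not support that: the SAP expects a balanced loss, and the calculation agrees.

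At the anticipated 5 years either side the loss is about 0.2%. The power table asks for 21,590 patients to detect 2% against 1.5%, so a window of a few weeks may carry little information on the primary outcomes. This stands for the main analysis if the window is wide. It does not settle the matter, because the rule picks the window by covariate balance and the only floor is 10 patients per group. Required sample size acts only as an upper cap.

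The effect of the age gap on outcomes is small. If risk rises 5% to 15% per year of age (an assumption), closing the gap by 6 days changes it by 6/365 of that, about 0.1% to 0.2% in relative terms.

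The excluded patients are also not ideal in every respect. Age is fixed at the test but onboarding follows, so someone just under 65 at test may turn 65 before onboarding. A small gap at the cut-off partly protects the treatment contrast. This stands, and it rules out deleting the exclusion without a matching sensitivity analysis.

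Finally, a reader might infer that NHS Digital can certainly supply the alternative at no cost. The SAP does not say so. It is a reasonable inference, since NHS Digital links the sources, calculates age, and limits the extract by exact birthday at the first test. But test dates come from two testing sources, so the first test must be settled before the variable is derived.

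**Conclusion.** The point holds as a minor design improvement. The form of the age request makes about six days' worth of patients around 65 unassignable. That is negligible at 5 years either side, but it is 43%, 21%, 11% and 5% of true windows of 1, 2, 4 and 8 weeks either side, which the stopping rule can readily select. The first window then compares mean ages 13 days apart instead of 7.

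This rests on a common reference date, even density of age near 65 and exclusion of unassignable patients only. The view that narrow windows are likely rests also on nine independent tests. It has not been shown that any estimate or conclusion would change, and the exclusion is no error of validity. Nor are all the nearest patients lost: about one in seven of those at the birthday itself are kept.

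**What to change.** Before extraction, ask NHS Digital to confirm whether it can supply, in place of age at a reference date, the signed number of completed weeks from the 65th birthday to the first positive test (0 = first week at or after 65, -1 = last week before). The anchor must be the birthday: 65 years is 3391.57 or 3391.71 weeks, so whole weeks of age at the test would still straddle the cut-off.

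If it can be supplied:
- remove the forced exclusion under Local randomisation approach;
- start window selection at weeks -1 and 0;
- add a sensitivity analysis omitting weeks -1 and 0, for patients who turn 65 between test and onboarding.

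If it cannot, say so in the SAP and keep the exclusion, noting that the first window then reaches almost two weeks either side.

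The cost is one line in the data specification, a few edited sentences and one extra sensitivity analysis. The new variable must replace the planned one, because supplying both could narrow birth date to less than seven days. It is undefined for patients onboarded without a positive test. They are only counted descriptively, and a coarse age band would serve.
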